3.2 Additional Variables of Interest

Variable	Description	Variables and Source	Specifications
Randomization assignment	hearing aid assignment	assign	Binary 1: unilateral 2: bilateral
Clinical site	Which site - Duke or Vanderbilt?	which_site Character version: which_site_ch	Binary 1: Vanderbilt 2: Duke
3 month chosen treatment	Hearing aid configuration at 3 months	ha_config_3m	Categorical 
 • Right • Left • Both

			
 • None • Missing
Gender		gender Character version: gender_ch	Categorical 
 • 1: male • 2: female • 3: other • 99: declined
Age	Age at baseline (years)	age_base Baseline visit is baseline_date	Continuous Years from baseline_date to dob Baseline visit is defined as aphab_base_date if non-missing, otherwise use date_moca
Race		race Character version: race_ch	Categorical 
 • 1: African American/Black • 2: White/Caucasian • 3: Asian • 4: Native American/Alaska Native • 5: Native Hawaiian/Pacific Islander • 6: More than one race • 99: Declined 
If cell counts are less than 10 for a given category, we will not report the exact cell count.
 
NIH racial categories: -American Indian/Alaska Native -Asian or Asian American -Black or African American -Native Hawaiian/Pacific Islander -White 

Ethnicity		ethnicity	Categorical 
 • 1: Hispanic or Latino

		Character version: ethnicity_ch	
 • 2: Not Hispanic or Latino • 999: Declined 
If cell counts are less than 10 for a given category, we will not report the exact cell count.

Income	Personal Income Last Year	income Character version: income_ch	
Categorical
 
 • 0: \$0 • 1: \$1 to \$9999 • 2: \$10,000 to \$24,999 • 3: \$25,000 to \$49,999 • 4: \$50,000 to \$74,999 • 5: \$75,000 to \$99,999 • 6: \$100,000 to \$149,999 • 7: \$150,000 or greater • 999: Prefer not to answer
Hearing Aid Health Insurance Benefits		benefits Character version: benefits_ch	
Categorical
 
 • 0: No • 1: Yes • 998: Not Sure
Marital Status		marital Character version: marital_ch	
Categorical
 
 • 1: married • 2: widowed • 3: divorced • 4: separated • 5: never married • 999: prefer not to answer
Living arrangements		living Character version: living_ch	
Categorical
 
 • 1: alone • 2: with spouse • 3: with spouse and others • 888: other • 999: prefer not to answer
Education		education Character version: education_ch	
Categorical
 
 • 1: less than high school • 2: high school • 3: some college • 4: 4-year degree

			
 • 5: graduate degree • 888: other • 999: prefer not to answer
Baseline Date Quarter		baseline_quarter	Categorical Put baseline date into quarters
Cognition (Screened via MoCA)	Adjusted MoCA score	total_moca	Continuous, 0-30 moca31 is a modifier for high school education If moca31=0, then total moca score is the sum of moca1 through moca30 If moca31=1, then total moca score is the minimum of 30 and the sum of moca1 through moca 31
Degree of Hearing Loss – Pure Tone Average	PTA in better ear	Right ear: pta_right Left ear: pta_left Better ear: pta_better	We will use the pure tone average in the better ear. Take the average at frequencies 500, 1000, 2000, 4000 in both ears. The lower average is the better ear.
Hearing loss classification		hearing_loss_class	Binary 
 • Mild: pta_better <= 40 • Moderate pta_better > 40
APHAB Change Score	Difference in aided APHAB scores at month 3 and unaided scores at baseline	aphab_change	Scale score – will need to calculate global communication scores at baseline (unaided) and 3 months (aided), subtract (3 months – baseline) A lower score on APHAB is better.

APHAB change score – binary, 3 months	Responders vs non-responders for primary APHAB outcome	
Decrease of 25 units: use aphab_change_responder
 
Decrease of 15 units: use aphab_change_responder_15
	
Patients with a decrease of at least 25 units (or 15 units for the sensitivity analysis) on the APHAB scale at month 3 will be considered “responders.” Patients not returning or who do not have a score at 3 months will be considered “non-responders.”
 
Binary (25 unit decrease):
 
 • 1 if aphab_change <=-25 • 0 else 
Binary (15 unit decrease);
 
 • 1 if aphab_change <=-15 • 0 else
IOI-HA	This is measured only at 3 and 6 months	Total score: ioiha_total_3m	
Total score: sum responses to questions 1-7 (should be on a range between 1-5).
 
Item 8 is self-perceived hearing difficulty used for normative purposes (currently not used as part of total score)
 
This is initially coded as 0 to 4 in REDCap – changed to 1-5
 
Currently, we’re treating IOI-HA total score as continuous, but this may need to be treated as ordinal.
 
Higher scores are better

SADL	
This is measured only at 3 and 6 months.
 
Note: the “sister” questionnaire at baseline is ECHO
	
Global score: sadl_global_3m
 
Positive effect subscale: sadl_positive_effect_3m
 
Service cost subscale: sadl_service_cost_3m
 
Negative features subscale: sadl_negative_features_3m
 
Personal image subscale: sadl_personal_image_3m
	
Questions 1 – 15 are used. This is scored from 1-7 (or reversed for questions 2, 4, 7, 13).
 
There are 4 subscales: Positive Effect, Service & Cost, Negative Features, Personal Image. For each subscale, the average score is calculated.
 
For the global score, this is the mean of the scores for all items (excluding questions 11 and 14 if applicable).
 
Higher scores are better (higher satisfaction).
 
See PCORI Scoring file for more details

SSQ	
This is measured at baseline, 3 months, and 6 months
	
Change score: ssq_change
 
Baseline:
 
Overall score: ssq_overall_base
 
Speech/hearing subscale: ssq_speech_hearing_base
 
Spatial/hearing subscale: ssq_spatial_hearing_base
 
Qualities of hearing subscale: ssq_qualities_of_hearing_base
 
3-Months:
 
Overall score: ssq_overall_3m
 
Speech/hearing subscale: ssq_speech_hearing_3m
 
Spatial/hearing subscale: ssq_spatial_hearing_3m
	
3 subscales: Speech is questions 1 – 14 (corresponds to the “pt1” variables). Spatial is 17 questions (corresponds to the “pt2” variables). Qualities is 18 questions (correspond to the “pt3” variables).
 
Overall score: mean of the items.
 
For instances where people mark NA and a value, if the value is 50, set as NA. If a value other than 50, use that value.
 
We will also create a change score as the difference in the

		Qualities of hearing subscale: ssq_qualities_of_hearing_3m	overall score between 3 months and baseline (3 months – baseline) Higher scores are better
HHI-E	This is measured at baseline, 3 months, and 6 months	Change score: hhie_change Baseline : Total score: hhie_total_base Situational subscale: hhie_situational_base Emotional subscale: hhie_emotional_base 3-Months : Total score: hhie_total_3m Situational subscale: hhie_situational_3m Emotional subscale: hhie_emotional_3m	Yes = 4 points, Sometimes = 2 points, and No = 0 points. Total scale score = sum of all 25 items Situational subscale: questions 1, 3, 6, 8, 10, 11 13, 15, 16, 19, 21, 23 Emotional subscale: questions 2, 4, 5, 7, 9, 12, 14, 17, 18, 20, 22, 24, 25 We will also create a change score as the difference in the total scale score between 3 months and baseline (3 months – baseline) Lower scores are better
Hours of Hearing Aid Use	Multiple time periods (every scheduled visit and unscheduled follow ups)	Right ear: r_avg_hrs_3m r_avg_hrs_3m_na (if right HA is NA) Left ear: l_avg_hrs_3m l_avg_hrs_3m_na	How many hours on average the right/left HA was worn. NA variables: value of 1 if that HA was NA
GHABP Unaided	GHABP is measured at baseline (unaided)	Question 2 average, 4 standard scenarios: ghabp_q2_4block_base Question 3 average, 4 standard scenarios: ghabp_q3_4block_base	For questions 2 and 3 (IF they answer yes to question 1), doing this separately by question: 1. Subtract 1, multiply by 25,

			
average answer to question across 4 standard scenarios
 
There are 6 scenarios (4 standard, 2 user-nominated)
 
Note that question 1 just asks if this scenario has happened – participants are only included in the averages if they answer “yes”
 
Lower scores are better for both questions

GHABP Aided	GHABP is measured at 3 months (aided)	
Question 2 average, 4 standard scenarios: ghabp_q2_4block_3m
 
Question 3 average, 4 standard scenarios: ghabp_q3_4block_3m
 
Question 4 average, 4 standard scenarios: ghabp_q4_4block_3m
 
Question 5 average, 4 standard scenarios: ghabp_q5_4block_3m
 
Question 6 average, 4 standard scenarios: ghabp_q6_4block_3m
	
For questions 3-6 (IF they answer yes to question 1), doing this separately by question:
 
 1. Subtract 1, multiply by 25, average answer to question across 4 standard scenarios 
Note: ignore current question 2 for analyses as it is non-standard but report on this in a descriptive table
 
There are 6 scenarios (4 standard, 2 user-nominated)
 
Note that question 1 just asks if this scenario has happened – participants are only included in the

			
averages if they answer “yes”
 
Higher/lower scores are better depending on question

Binaural loudness summation	Baseline only CSL level right CSL level left CSL level both	binaural_r_base binaural_l_base binaural_both_base	Continuous
Dichotic digit test	Baseline only Right ear directed Left ear directed Free recall both ears Right ear free recall Left ear free recall	dichotic_r_base dichotic_l_base dichotic_free_both_base dichotic_free_r_base dichotic_free_l_base	Continuous
Speech and Noise Test	Baseline (unaided) and 3-months (aided) Speech and noise 0 degrees (collocated) Speech left, noise right Noise left, speech right	
Baseline: sin_collocated_base sin_right_base sin_left_base
 
3-Months: sin_collocated_3m sin_right_3m sin_left_3m
 
Change: sin_collocated_change sin_r_change sin_l_change
 
May also want change scores for speech to aided side and speech to unaided side
	
Continuous
 
Change scores: 3m-baseline for each of collocated, speech left/noise right, noise left/speech right
 
Positive values for unaided/aided variables indicate speech is louder than noise; negative indicate speech is under the noise
 
For unilateral assigned, also have speech to aided side (advantage) and speech to unaided side (disadvantage).
 
Speech to aided (advantage):
 
 • If assigned R, this is noise left, speech right

			
 • If assigned L, this is speech left, noise right 
Speech to unaided (disadvantage):
 
 • If assigned R, this is speech left, noise right • If assigned L, this is noise left, speech right 
Lower scores are better

Auditory Working Memory	
Unaided and Aided (3 months)
 
Recognition, judgement, recall
	
Change scores: warrm_recog_change warrm_recall_change
 
Baseline: warrm_recog_base warrm_recall_base warrm_judge_base
 
3-Months: warrm_recog_3m warrm_recall_3m warrm_judge_3m
	
Continuous
 
Sum questions 2-6 for each tasks (recognition, judgement, recall) separately and get a % correct (out of 20)
 
Construct change scores as difference between 3 months and baseline for recognition and recall.
 
Judgement is more of a sanity check (<90% means they probably aren't engaged)
 
Higher scores are better

ECHO	
Baseline only
 
Note: this is the "sister" questionnaire to SADL (aided)
	
Global score: echo_global_base
 
Positive effect subscale: echo_positive_effect_base
 
Service cost subscale: echo_service_cost_base
 
Negative features subscale: echo_negative_features_base
 
Personal image subscale: echo_personal_image_base
	
Questions 1 – 15 are used. This is scored from 1-7 (or reversed for questions 2, 4, 7, 13).
 
There are 4 subscales: Positive Effect, Service & Cost, Negative Features, Personal Image. For each subscale, the average score is calculated.

			For the global score, this is the mean of the scores for all items (excluding question 11 if applicable). Higher scores are better (higher expectations). See PCORI Scoring file for more details
--	--	--	---

4 Statistical Analysis Plan

Analysis: To be completed by December 31, 2024.

4.1 Descriptive Table of Switched Configuration Status by Assigned Treatment

Analysis: This will be descriptive. As appropriate, we will present the frequency with percentage (see Table 1). Note that “switched configuration” will be defined as yes for those who switched configuration at 3 months and will be defined as no for those who did not switch configuration at 3 months.

Table 1: Switched HA Configuration and Choice vs. Assigned Treatment

	Assigned Unilateral Left (N=XXX)	Assigned Unilateral Right (N=XXX)	Assigned Bilateral (N=XXX)
Switched Configuration at 3 Months			
No	XXX (%)	XXX (%)	XXX (%)
Yes	XXX (%)	XXX (%)	XXX (%)
Missing	XXX (%)	XXX (%)	XXX (%)
Hearing Aid Configuration Choice at 3 Months			
Unilateral Left	XXX (%)	XXX (%)	XXX (%)
Unilateral Right	XXX (%)	XXX (%)	XXX (%)
Bilateral	XXX (%)	XXX (%)	XXX (%)
None	XXX (%)	XXX (%)	XXX (%)
Missing	XXX (%)	XXX (%)	XXX (%)

4.2 Investigate if assigned treatment influences switching at 3 months

Analysis: This will be done using assigned treatment for patients who have information on switching status at 3 months. This analysis will be performed using logistic regression where the outcome is switching status (the probability modelled is switching). The only covariate included in this model will be assigned treatment. A similar model will be fit for the binary outcome 6M HA configuration choice (unilateral vs bilateral).

$$\text{Hearing Aid Switching Status} = \beta_0 + \beta_1 * \text{treatment assignment}$$

**Table 2 Logistic Regression OR Estimate for HA Assignment
Probability Modelled: Switched HA Configuration**

Covariate	OR	95% C.I.	P-Value*
Hearing Aid Assignment (Reference: Bilateral)			
Unilateral	XXX	(XXX , XXX)	XXX

*Using XXX statistic

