hearing loss and their significant others. Furthermore, the results of this study will inform hearing health strategies at the population level by demonstrating real-world influences of patient engagement and communication benefit. Specifically, in order to make appropriate clinical recommendations, information regarding how unilateral versus bilateral hearing aids affect patient directed real-world outcomes in listeners with mild-to-moderate hearing loss will be gathered. We emphasize real-world outcomes in the proposed study because (1) real-world outcomes are more likely to be relevant to public health and (2) the literature has suggested that hearing outcomes measured in the laboratory often do not translate to the real world.⁷⁸⁻⁸¹ To minimize recall bias, hearing aid success will be also measured *in situ* (i.e., in natural environment) using a novel smartphone-based Ecological Momentary Assessment (EMA) system. Recent data have indicated that the *in-situ* self-reports collected using a smartphone EMA system are more sensitive, and potentially more valid, than retrospective questionnaires.^{82,83} The knowledge gained from this study has the real potential to change the dialogue for the recommendation of unilateral versus bilateral hearing aids. This knowledge is especially timely given the nascent federal law requiring the development of a class of over-the-counter hearing aids. The cost of the over-the-counter hearing aid is still likely to be substantial. Patients want the best value for their money, and a second hearing aid may not be incrementally better for the patient when they are confronted with the cost. Patients will soon be faced with making the best the choice of cost and functionality for themselves in their daily lives.

4. Design & Procedures: This is a randomized, parallel-group, two-phase, clinical trial (RCT) with two treatment arms including: (1) a bilateral hearing aid fitting group, and (2) a unilateral hearing aid fitting group. This RCT design will allow us to determine whether or not bilateral hearing aids are more beneficial than a unilateral hearing aid.

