2.3 Data Acquisition

Fill in all relevant information:

Study design	Randomized controlled trial with 2 arms (bilateral hearing aid, unilateral hearing aid) Note: Randomization was stratified by clinical site.
Data source/how the data were collected	Screening information pulled from EHR data Baseline surveys captured via in-person interview and recorded in REDCap

Contact information for team member responsible for data collection/acquisition	All data access is through [REDACTED] [REDACTED]. Questions on data validity will go to PI: [name] ([contact])
Date or version (if downloaded, provide date)	10.17.2024
Data transfer method and date	Direct data extraction from REDCap
Where dataset is stored	REDCap Extracted data and analytic datasets are stored on a secure drive in the CRU folder: \\duhs-vclin-nc1\dusom_biostats_fs\Data\BiostatsCore\CRU\Head and Neck\[name]\PCORI_Pro00106077\Data pulls

Notes:

Description:
[insert]

3 Outcomes, Exposures, and Additional Variables of Interest

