4.3 Investigate what predicts switching at 3 months

Analysis: This will be done for all randomized patients who are not missing scores or other predictors of interest. This analysis will be performed using the LASSO for logistic regression where the outcome is switching status (the probability modelled is switching) or 6M HA configuration choice (modelled probability is unilateral). Covariates (denoted generally as L below) to include in these models are age at baseline, gender, pure tone average in the better ear, baseline global HHI-E, baseline APHAB Global, baseline APHAB AV, binaural loudness summation (both), REAfree (Dichotic Digits, free right minus free left), REAdirect (Dichotic Digits, direct right minus direct left), cognitive effect LE (Dichotic Digits, direct left minus free left), cognitive effect RE (Dichotic Digits, direct right minus free right), AWARRM recall, and education-adjusted MoCA total score. The selected variables, their odds ratios, and 95% confidence intervals constructed from post-selection inference methods (R package ‘selectiveInference’) will be reported.

$$\text{Hearing Aid Switching Status} = \beta_0 + \beta_L * L$$

**Table 3: Logistic Regression OR Estimates
Probability Modelled: Switched HA Configuration**

Covariate	OR	P-S 95% C.I.
Covariate 1 (Ref: category)		
Category x....	XXX	(XXX , XXX)
Covariate 2	XXX	(XXX , XXX)

4.4 Describe patient characteristics for those who switch their HA configuration vs. those who don't

Analysis: The characteristics from “non-switchers” will be compared to “switchers” with the use of a “Table 1”. As appropriate, we will present the mean with standard deviation (SD), median with interquartile range (IQR), and ranges (min and max), or frequency with percentage. A similar table will be constructed with participants stratified by 6M HA configuration choice.

Table 4: Patient Characteristics for Non-Switchers and Switchers

	Non-Switchers (N=XXX)	Switchers (N=XXX)
Clinical Site		
Duke	XXX (%)	XXX (%)
Vanderbilt	XXX (%)	XXX (%)
Gender		
Female	XXX (%)	XXX (%)
Male	XXX (%)	XXX (%)
Other	XXX (%)	XXX (%)
Age at Baseline Visit		
N	XXX	XXX

Missing	XXX	XXX
Mean (SD)	XXX (XXX)	XXX (XXX)
Median	XXX	XXX
Q1, Q3	XXX , XXX	XXX , XXX
Range	XXX - XXX	XXX - XXX
Race		
American Indian/Alaska Native	XXX (%)	XXX (%)
Asian	XXX (%)	XXX (%)
Black or African American	XXX (%)	XXX (%)
White	XXX (%)	XXX (%)
More than one race	XXX (%)	XXX (%)
Native Hawaiian/Pacific Islander	XXX (%)	XXX (%)

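### The switching and final-choice models leave out clinical site, the randomisation stratum: a slight attenuation in 4.2, a conditional risk of falsely flagged predictors in 4.3, and a cheap repair for both

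*SAP*

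**What the plan says.** The Hearing Aid Choice and Switching SAP, section 2.3, records the design: "Note: Randomization was stratified by clinical site". Section 4.2 then fits a logistic regression of 3-month switching on assignment. It states that "The only covariate included in this model will be assigned treatment", and it plans a similar model for the 6-month choice of one or two aids.

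Section 4.3 runs a LASSO logistic regression for switching or 6-month choice on a closed list. The list begins "Covariates (denoted generally as L below) to include in these models are age at baseline, gender, pure tone average in the better ear" and ends "AWARRM recall, and education-adjusted MoCA total score". It has 13 candidates: age, gender, better-ear pure-tone average, HHI-E, APHAB global, APHAB AV, binaural loudness summation, four dichotic-digit contrasts, AWARRM recall and MoCA. Site is not among them.

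Two cost-related variables are defined in section 3.2 of the same SAP, "Personal Income Last Year" and "Hearing Aid Health Insurance Benefits", but they are not candidates either. Site, income and insurance benefit appear by switching status only in the descriptive Table 4 of section 4.4, and a similar table is planned by 6-month choice. No reason is given for leaving them out of the models.

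Elsewhere the plan does include site: in the primary linear model (Primary Analysis SAP, 4.3), the responder logistic models (same SAP, 4.6) and the EMA mixed models (EMA SAP, 4.2).

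**The concern.** The responder model in the Primary Analysis SAP is the same kind of model as 4.2, a logistic regression on assignment, and it carries site. The switching model does not, although switching could well depend on local practice. Under Protocol section 4, the audiologists at each site do the education, fitting, fine-tuning and refitting.

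The two sections carry different risks. In 4.2 the question is whether the assignment odds ratio is distorted. In 4.3 the question is whether a candidate whose distribution differs between Duke and Vanderbilt could pick up a site difference in switching and be reported as a patient predictor. Post-selection intervals allow for the selection step. They do not allow for a missing common cause.

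A smaller matter concerns cost. Participants pay for the aids or use insurance (Protocol section 4), and Protocol section 3 says "Patients want the best value for their money, and a second hearing aid may not be incrementally better for the patient". The 4.3 model cannot select a cost-related variable, because none is offered to it.

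**Working it through.** The documents state no switching rate, power or site difference for these models, so there is no planned figure to reproduce. The sizes below rest on stated assumptions: two equal sites and, for 4.3, the planned enrolment of 350 (Protocol section 6).

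**Section 4.2: odds ratio with site omitted.** Assignment is balanced within site, so the model without site estimates the ratio of the site-averaged odds:

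OR(no site) = odds(mean of p1 over sites) / odds(mean of p0 over sites), where odds(p1) = 3 × odds(p0) within each site.

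Worked for reference-arm switching of 20% and 40%:
- Reference odds are 0.25 and 0.667. The mean probability is 0.30, with odds 0.4286.
- Tripled odds are 0.75 and 2.0, giving probabilities 0.4286 and 0.6667. The mean is 0.5476, with odds 1.2105.
- Ratio: 1.2105 / 0.4286 = 2.82.

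| Reference-arm switching at the two sites | Within-site OR | OR with site omitted |
|---|---|---|
| 25% / 35% | 3.0 | 2.96 |
| 20% / 40% | 3.0 | 2.82 |
| 15% / 45% | 3.0 | 2.61 |

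A second setting gives the same picture. With 15% switching in the reference arm at the lower site and a within-site OR of 4, omitting site gives 3.95, 3.86 and 3.65 for site odds ratios of 1.5, 2 and 3.

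Under no treatment effect (348 participants, 25% mid-point rate, site OR 3, 2,000 simulated trials), type I error was 0.049 without site and 0.058 with it. Both are near 0.05.

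**Section 4.3: a predictor with no effect of its own.** The simulation used 350 participants, a 25% mid-point switching rate and 1,000 trials per cell. The predictor's mean differs by d standard deviations between sites. The test is a one-predictor logistic Wald test at 5%, used in place of the LASSO.

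| Site OR for switching | d | Flagged, no site | Flagged, with site |
|---|---|---|---|
| 1 | 0.2 to 0.5 | 0.043 to 0.049 | 0.043 to 0.050 |
| 1.5 | 0.2 / 0.3 / 0.5 | 0.054 / 0.065 / 0.067 | 0.050 / 0.054 / 0.040 |
| 2 | 0.2 / 0.3 / 0.5 | 0.050 / 0.082 / 0.125 | 0.053 / 0.054 / 0.061 |
| 3 | 0.2 / 0.3 / 0.5 | 0.063 / 0.095 / 0.180 | 0.043 / 0.047 / 0.045 |

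The largest spurious odds ratio was about 1.14 per SD. Setting overall switching at 20% and 40% by site, with d = 0.5, gives about 16% flagged and 1.12 per SD. That site OR is 0.667 / 0.25 = 2.67, so the result falls where expected between the rows for 2 and 3.

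**Price of more terms in 4.3.** Each listed candidate is counted as one parameter. Site adds 1, three-level income group 2 and three-level insurance benefit 2, so 13 becomes 18. Switching rates of 20% and 40% are assumed.

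| Switching | Events (of 350) | Per parameter, 13 | Per parameter, 18 |
|---|---|---|---|
| 20% | 70 | 5.4 | 3.9 |
| 40% | 140 | 10.8 | 7.8 |

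Site alone gives 14 parameters: 70/14 = 5.0 and 140/14 = 10.0.

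**The case against.** The strongest reply has four parts.

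*Site cannot confound randomised assignment.* This stands. The 4.2 estimate is a valid odds ratio averaged over sites. A reader might infer that leaving out site biases the treatment comparison or turns site habits into patient predictors there. It does neither: 4.2 has no patient predictors, and its type I error is near nominal.

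*Other secondary analyses omit site too.* The 3-month and 6-month SAPs compare arms by t-test or Kruskal-Wallis test. This also stands, so the omission is not unique. It does not explain why two logistic regressions on assignment in the same programme differ.

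*The 4.3 risk is hypothetical.* Protocol section 4 calls for standardised education and real-ear verification, both sites share eligibility criteria, and nothing shows that switching or any candidate differs by site. The one-predictor test is also not the planned procedure. All of this limits the size of the point. It does not argue against including a stratum that is already recorded.

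*Cost is neither ignored nor ranked first.* A reader might infer that the trial fails to examine the protocol's leading explanation for choosing one or two aids. The documents do not support that. Protocol section 3 stresses cost, but it also lists patient need, asymmetry, cosmetics and finance together without ranking them. Table 4 shows income and insurance benefit by switching status, and the focus groups discuss the reasons for the final choice. What remains is narrower: cost is absent from the multivariable analysis, and no reason is given.

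**Conclusion.** The point holds as a modest one. Site, the randomisation stratum, is missing from both 4.2 models and from the 4.3 candidate list, while the primary, responder and EMA models include it.

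For 4.2 the consequence is slight attenuation, 3.0 to between 2.61 and 2.96 under the assumed site differences, and no false-positive problem. For 4.3 the risk is conditional. Both switching and the predictor must differ by site, and the flagging rate then ranges from essentially nominal when the differences are small to 18% at a site OR of 3 and a 0.5 SD difference. It returns to about 4% to 6% once site is in the model. These rates come from a one-predictor test, so they indicate direction and rough size and are not the error rate of the planned LASSO.

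That the 4.3 model cannot select cost follows from its list and needs no assumption. Whether cost variables belong there is more open to judgement, because cost is one prominent factor among several and the added terms reduce events per parameter.

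**What to change.** **Main change.** Add clinical site to both 4.2 models (3-month switching and 6-month choice) and give it a row in Table 2, as the responder model does. In 4.3, keep site in the model unpenalised for both outcomes. This costs one parameter per model and uses data already collected.

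**Secondary suggestion.** Offer the LASSO hearing-aid insurance benefit and the three-level income group defined in section 3.3 of the Primary Analysis SAP, or state why they are excluded. State how the not-sure and prefer-not-to-answer levels are handled. With site, this takes 13 parameters to 18 and lowers events per parameter from about 5.4–10.8 to 3.9–7.8 if 20% to 40% of 350 switch. The SAP should acknowledge that.

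The SAP set completion of this analysis for December 31, 2024. If it has already been run, keep the planned results and report the version with site, and with the cost candidates if added, as a labelled additional analysis.
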